8.9. Subgroup Analyses

Subgroup analyses by age group, gender, and race (using all available categories) will be performed for the primary endpoint and the change from baseline to Week 52 in % predicted FVC.

In addition, the following subgroups will be analyzed for the primary endpoint and the change from baseline to Week 52 in % predicted FVC, unless otherwise specified:

- ERT status (categorized as: ERT-experienced versus ERT-naïve)
This subgroup analysis will apply to the primary and key secondary endpoints, % predicted SVC, as well as for the overall adverse event (AE) overview table, summary of treatment-emergent AEs by system organ class and by preferred term, and PD endpoints.
- Baseline 6MWD (categorized as: 75 to < 150 meters, 150 to < 400 meters, ≥ 400 meters)
Note that for this subgroup analysis, categories may be collapsed depending on the actual number of subjects in each category, eg, 75 to < 150 meters and 150 to < 400 meters may be combined into 75 to < 400 meters.
- Baseline 6MWD < *median value*, baseline 6MWD ≥ *median value*
- Baseline FVC < *median value*, baseline FVC ≥ *median value*
- Regions (North/South America, Europe, Asia Pacific)
- ERT duration categorized as: 2 to < 3, 3 to < 5, and ≥ 5 years
- History of IARs (Yes, No)

All subgroup analysis results will be presented by forest plots. The p-values for the treatment-by-subgroup interactions will be presented together in a tabular form.

Note that subgroup analyses will not be performed if the size of the specified subgroup category is small and the analyses will not be meaningful.

9. ANALYSIS OF SAFETY

Safety will be evaluated through the analyses of AEs, clinical safety laboratory data, vital signs, physical examination, electrocardiogram (ECG), and concomitant medications.

Safety analyses will be based on the safety population. Safety data will be summarized using counts and percentages for categorical data and using descriptive statistics (n, mean, SD, median, Q1, Q3, minimum, and maximum) for continuous data. No formal statistical tests will be performed.

Infusion-associated reactions in the ATB200/AT2221 arm will be compared in frequency to the alglucosidase alfa/placebo arm in this study.

Adverse events will be coded by system organ class (SOC) and preferred term (PT) using MedDRA version 20.1 or higher.

Concomitant medications and nondrug therapies will be summarized by treatment group. Concomitant medications and nondrug therapies will be coded using WHO DDE, March 2017 or later.

9.1. Treatment-emergent Adverse Events

Summary of adverse events will be based on TEAEs. A TEAE is defined as any event that started or changed in the severity on or after the first dose of study drug.

For AEs occurring on Day 1, if the start time of the event is missing or after the administration of the first dose of study drug, the event will be considered a TEAE.

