8.2. Duration of Study

The study will consist of a screening period up to 30 days, a 12-month treatment period, and a 30-day safety follow-up period. Subjects who missed visits due to COVID-19 related quarantines, travel restrictions, and risk of infection may be enrolled longer than 12 months in the study. In addition, subjects who discontinue study drug for any reason will be followed for up to 12 months for monitoring of immunogenicity; these results will be reported separately.

Subjects who complete this study will have the option to participate in an open-label extension study to receive ATB200/AT2221 under a separate protocol.

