12.3.8. Adverse Events

Reporting of AEs begins after written informed consent is provided, including study-related events that occur as a direct result of a study procedure (eg, if a subject falls during a functional assessment) and IARs. As required by their institutions, investigators will be responsible for reporting AE information to their IRB, IEC, or REB (see Section 13). If the start date of an AE is prior to enrollment in this study, it should be captured as medical history.

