13. ADVERSE EVENTS AND SERIOUS ADVERSE EVENTS

13.1. Definitions

13.1.1. Adverse Events

An AE is defined as any untoward medical occurrence in a patient or clinical investigation subject administered a pharmaceutical product, biologic (at any dose), or medical device, which does not necessarily have a causal relationship with the treatment. Therefore, an AE can be any unfavorable and unintended sign, symptom, or disease temporally associated with the use of a medical product, whether or not considered related to the medical product.

According to this protocol, expected or anticipated evolution of the disease under treatment will be evaluated as part of the disease symptom assessment. Changes in Pompe disease symptoms must be reviewed by the investigator or a medically qualified subinvestigator and recorded as “clinically significant” or “not clinically significant” in subjects’ source records (see [Appendix 2](#)). Expected or anticipated changes in the clinical condition may not qualify as AEs. However, if there is a clinically relevant worsening of a sign or symptom of the disease under treatment and the outcome fulfills the definition of an AE, it must be reported as directed in the protocol.

Any AE that begins after the first dose of study drug will be considered a treatment-emergent AE.

Subjects experiencing AEs should be followed up until their health has returned to baseline status or stabilized.

AEs include the following:

- the onset of new signs, symptoms, conditions, and illnesses
- exacerbation of pre-existing conditions or illnesses
- abnormal laboratory findings deemed clinically significant by the investigator
- physical examination changes deemed clinically significant by the investigator
- abnormal medical evaluation findings (eg, ECG) that are not documented at the Screening Visit and/or, in the investigator’s opinion, represent a clinically significant change in the subject’s health during study participation
 - Screening medical evaluation findings (eg, ECG) that were not previously provided as medical history and that can be determined as starting prior to the Screening Visit are not considered AEs and will be recorded as medical history.

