13.1.2. Serious Adverse Events

A serious adverse event (SAE) is any AE that:

- Results in death
- Is life-threatening
 - An AE, in the view of either the investigator or Amicus, that places the subject at immediate risk of death. It does not include an AE that, had it occurred in a more serious form, might have caused death.
- Requires inpatient hospitalization or prolongs existing hospitalization
 - Hospitalization signifies that the subject has been admitted, regardless of duration, for observation and/or treatment that would not have been appropriate in a physician's office or outpatient setting.
 - Hospitalizations for elective or preplanned treatment of a pre-existing condition do not have to be reported as SAEs, provided that
 - the condition is documented in the subject's medical history and has not worsened since the ICF was first signed, and
 - the planned procedure is documented in the subject's eCRF at the Screening Visit
 - Note: Outpatient procedures performed in a hospital do not qualify as an SAE.
 - Emergency room/department or outpatient treatments that do not result in admission do not have to be reported as an SAE, unless another SAE criterion is met.
 - Events assessed and treated in these circumstances should be captured as AEs.
 - Hospitalizations solely based on logistics (eg, subject is admitted due to limited hospital accessibility for what would otherwise be an outpatient procedure) do not have to be reported as SAEs.
 - These hospitalizations should be clearly defined as such in the subject's source record.
- Results in persistent or significant incapacity or substantial disruption of the ability to conduct normal life functions, as decided by the investigator
- Is a congenital anomaly/birth defect

An important medical event that may not result in one of the abovementioned serious outcomes may be considered an SAE when, based on appropriate medical judgment, it may jeopardize the subject and may require medical or surgical intervention to prevent one of the serious outcomes. Examples of such medical events include allergic bronchospasm requiring intensive treatment in an emergency room or at home, blood dyscrasias or convulsions that do not result in inpatient hospitalization, or development of drug dependency or drug abuse.

For all subjects, AEs and SAEs will be reported from time of informed consent signing, until 30 days after the last dose of study drug.

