13.2. Reporting of Adverse Events

Information regarding AEs is to be obtained by questioning or examining the subject.

Adverse events will be recorded in the eCRF and subject's source record beginning from the time written consent is provided until 30 days after the last treatment visit.

A single diagnosis should be entered when known. If a clear diagnosis cannot be determined at the time of the eCRF and subject's source record entries, each sign and symptom must be recorded individually, until a final diagnosis is established. Pompe-related conditions, signs, symptoms, etc, that are present in the subject's medical history at the Screening Visit should only be reported as AEs if they worsen (ie, increase in severity) from the Screening Visit.

For each AE reported, the date and time the event started and ended, action taken, outcome (resolved, resolved with sequelae, ongoing, or fatal), and severity must be noted.

All subjects who have AEs, whether or not considered associated with the use of study drug, must be monitored to determine the outcome. The clinical course of the AE will be followed up according to accepted standards of medical practice, even after the end of the period of observation, until a satisfactory explanation is found or the investigator considers it medically justifiable to terminate follow-up. Should the AE result in death, a full pathologist's report should be supplied, if possible. For all AEs that require or result in subject discontinuation from the study, relevant clinical assessments and laboratory tests will be repeated as clinically appropriate, until final resolution or stabilization of the event(s).

If the investigator considers it necessary to report a nonserious AE in a study subject more than 30 days after the last visit, he or she should contact Amicus to determine how the AE should be documented and reported.

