2. INTRODUCTION

This statistical analysis plan (SAP) describes the planned data derivations, analyses, and statistical methods to be performed for Study ATB200-03. It is based on:

- Protocol for ATB200-03 Amendment 3 dated 14 August 2020
- Amicus standard operating procedure (SOP) ATCRA-SOP-AT-008
- Good Clinical Practices (GCP) and International Conference on Harmonisation (ICH) guidelines E9 (Statistical Principles for Clinical Trials)
- Discussions with Regulatory Authorities

The purpose of this document is to provide details on study populations and on how the variables will be derived, how missing data and intercurrent events will be handled, as well as details on statistical methods to be used to analyze the efficacy and safety data from Study ATB200-03.

The document may evolve over time to reflect protocol amendments, regulatory discussions, and other important changes. However, the final SAP will be finalized, approved by the Sponsor, and placed on file before the database is locked. The data analyses and statistical methods specified in the final SAP supersede those described in the study protocol. Deviations from the final approved plan will be noted in the clinical study report.

Pharmacokinetic (PK) and immunogenicity analyses will be covered in separate analysis plans.

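### The SAP's TEAE definition turns on a severity change in either direction, so an adverse event that starts in screening and eases after Day 1 is literally treatment-emergent

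*SAP*

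**What the plan says.** SAP section 9.1 sets the rule: "A TEAE is defined as any event that started or changed in the severity on or after the first dose of study drug". The sentence before it makes the flag decisive for reporting: "Summary of adverse events will be based on TEAEs".

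Protocol section 13.1.1 defines the same term by onset alone: "Any AE that begins after the first dose of study drug will be considered a treatment-emergent AE". It has no severity limb.

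The SAP governs where the two differ on analysis. Section 2 states: "The data analyses and statistical methods specified in the final SAP supersede those described in the study protocol".

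Three protocol provisions decide which events can be in the data before dosing:

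- Section 13.1.2, on when collection starts: "AEs and SAEs will be reported from time of informed consent signing".
- Section 12.3.8, on earlier events: "If the start date of an AE is prior to enrollment in this study, it should be captured as medical history".
- Section 13.2, on Pompe-related conditions already in the medical history at screening, which "should only be reported as AEs if they worsen (ie, increase in severity) from the Screening Visit".

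**The concern.** A treatment-emergent flag is meant to separate what appeared or got worse on treatment from what was already there. A limb that any severity change satisfies also admits events that were already there and got better, so an improvement is tabulated as an emergent harm.

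The flag feeds every table listed in SAP section 9.1.2: the overview, the system organ class and preferred term tables, and the splits by severity and by relationship. It also feeds the adverse event subgroup tables by ERT status in section 8.9. Under section 9.1.6.4, a flagged event with no relationship assessment would also be shown as related. A programmer who reads the text as meaning worsening would depart from the written plan, so two programmers could flag different events from the same data.

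**Working it through.** No arithmetic applies: no sample size, error rate or variance enters the point, and the documents give no number of adverse events with onset before dosing. The check is to apply the written rules to each type of event.

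**Can an adverse event start before dosing and still be in the data?** Yes. Collection begins at consent, and the schedule of assessments (Protocol Table 10) has adverse events collected at both screening visits. On the length of the window, Protocol section 8.2 says: "The study will consist of a screening period up to 30 days". Section 12.2.1 allows up to two rescreens, with a new consent needed only after 1 month, so the interval from consent to first dose can exceed 30 days for some subjects. ERT-experienced subjects stay on alglucosidase alfa during screening (Protocol section 8.1), which is one possible source of such events.

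**How is each case classified?**

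| Event | SAP 9.1 | Protocol 13.1.1 |
|---|---|---|
| Starts after first dose | TEAE | TEAE |
| Starts between consent and first dose, severity rises after dosing | TEAE | Not a TEAE, unless recorded as a new event |
| Starts between consent and first dose, severity falls after dosing | TEAE | Not a TEAE |
| Starts between consent and first dose, severity unchanged | Not a TEAE | Not a TEAE |

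The third row is the problem. The second row shows that the SAP is also broader than the protocol in a sensible way: it picks up worsening, which the protocol's onset rule misses.

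**Does another SAP rule remove the third row?** Sections 9.1.1 (reporting period), 9.1.2 (tabulation) and 9.1.6.1 (partial and missing dates) do not restrict the direction of change. The worst-case rule in 9.1.2 selects which severity is shown within a class or term; it does not decide which events qualify.

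**What lies outside the third row?** An event that started before enrollment is medical history under Protocol section 12.3.8. A Pompe-related condition in the history is reported as an adverse event only on worsening under section 13.2. Neither enters the adverse event data by improving.

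**What else must hold?** The database must record a severity change within an ongoing event. Protocol section 13.2 requires a severity for each event, and neither document says how a later change is captured.

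**The case against.** The strongest reply is that the rule may never operate. If one severity is stored per event, a decrease cannot trigger it. This stands as a condition on the effect, though not as a defence of the wording, because the severity limb was presumably written to be used.

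Second, the consequence is limited. SAP section 9 provides no formal safety tests. Section 9.1.2 counts a subject once per class and once per term, so an extra event changes incidence only where that subject has no other qualifying TEAE in the row. All adverse events are listed with onset date and study day, so onsets before dosing stay identifiable. Over-inclusion also fits the SAP's cautious handling elsewhere, such as treating missing severity as severe. All of this stands, and it keeps the point minor. Caution about missing data is nevertheless different from counting a recorded improvement as emergent.

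Third, a difference from the protocol is not in itself an error, since the SAP supersedes it for analysis. That is correct. The fault lies in the SAP rule itself.

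A reader might also infer that improvement in any pre-existing condition becomes a TEAE, or that the protocol's TEAE definition counts pre-existing conditions only if they worsen. The documents support neither. Medical history is kept out, and the worsening wording in Protocol section 13.2 is a reporting rule for Pompe-related history rather than part of the TEAE definition.

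**Conclusion.** The wording is wrong as written, with a narrow reach. It misclassifies adverse events that begin between consent and first dose, are ongoing at Day 1 and then lessen, if the severity change is recorded. Within an arm it can only add TEAEs.

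The size cannot be estimated from the documents. Balance between arms cannot be assumed either: the easing happens after randomization, so the arm in which screening-onset events ease more often would show more TEAEs. A reader might infer that the inflation is similar in both arms, or that it distorts the main safety endpoint. Nothing in the documents supports the first. On the second, Protocol section 15.1.5 and SAP section 3.3.6 list TEAE incidence alongside serious events, events leading to discontinuation, infusion-associated reactions and other abnormalities, and rank none of them as main.

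The conclusion assumes that enrollment in Protocol section 12.3.8 means consent, which fits the collection of adverse events at the screening visits. A later meaning would narrow the window further.

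**What to change.** Before database lock, replace the severity limb in SAP section 9.1 with *worsened (increased) in severity* and leave the rest of the sentence as it is. Add a note that this deliberately extends the protocol's onset-only definition, because the revised text will still differ from Protocol section 13.1.1. It would also help to state how a severity change in an ongoing event is recorded, and which severity is tabulated for an event that qualifies through worsening.

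The cost is a few words and, if the flag is already programmed, a check of its logic. No new data are needed and no efficacy analysis is touched.

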9.1.1. Adverse Event Reporting Period

In general, TEAEs that occur more than 30 days from the last dose of study drug will not be counted.

- For subjects who permanently discontinue study drug prematurely or who complete the treatment period and do not continue or enter the optional OLE study, ATB200-07, their AEs will be tabulated up to 30 days after the last treatment visit in Study ATB200-03. Their TEAE tabulation period (days) is calculated as:
$$(\text{last dose date of study drug} + 30 \text{ days}) - \text{first dose date} + 1.$$
- For subjects who are confirmed to have a positive result for anti-rhGAA antibodies at the time of discontinuation and up to the 30-day safety follow-up visit, they will continue to have follow-up immunological testing for up to 12 months (ie, at 6 months and 12 months) after the last dose date of study drug, but the AE collection will be up to 30 days from the time of study discontinuation.

In order to generate summary results for the clinical study report (CSR), the summary will use only the events (ie, AEs and immunogenicity) that occurred within the first 30 days after the last dose of study drug in Study ATB200-03. The additional potential immunogenicity events from Month 1 to Month 12 post the date of last dose of study drug will be reported as an addendum to the ATB200-03 CSR.

9.1.2. Summary of Treatment-emergent Adverse Events

The overall summary of TEAEs table will be presented by treatment group and for all treated subjects using the number and percentage of subjects. The following events will be summarized:

- Any treatment-emergent adverse events (any TEAE)
- Treatment-emergent serious adverse events (TESAEs)
- TEAEs leading to study drug discontinuation
- TEAEs related to study drug (ie, treatment related TEAEs)
- TEAEs related to study drug and leading to study drug discontinuation
- TESAEs leading to study drug discontinuation
- TESAEs related to study drug (ie, treatment related TESAEs)
- TESAEs related to study drug and leading to study drug discontinuation
- Deaths

In addition, summary tables will be presented for each of the individual bulleted items listed above.

The number and percentage of subjects who experienced TEAEs will be presented by SOC and by PT within SOC for each treatment group. The table by SOC and PT will be repeated, one with the PTs within SOC sorted according to descending order of the ATB200/AT2221 group, and another the PTs sorted alphabetically within the SOCs. A subject will be counted only once within the same SOC and within the same PT.

The cumulative number and percentage of subjects with TEAEs will be summarized by severity (mild, moderate, severe) for each treatment group, and by relationship to study drug ('related' vs 'not related') for each treatment group. If a subject experienced more than 1 TEAE within different severity or relationship categories within the same SOC/PT, only the worst case (worst severity and related TEAE) will be reported.

All AEs will be provided in a listing that will include the subject identifier, SOC, PT, and the reported term, date of onset and study day, date of resolution and study day, the seriousness, the severity, the relationship to each individual study drug (for TEAEs), duration, the action taken, and the outcome. All TEAEs will be flagged in the listing.

Listings will also be generated for deaths, SAEs, and discontinuations due to TEAEs.

9.1.3. TEAEs Reported as Infusion-associated Reaction

For any AE, the reporting investigator is requested to enter on the AE eCRF whether the AE is deemed to be an infusion-associated reaction and determine the relationship to each of the study drug components (ATB200, AT2221, alglucosidase alfa, and placebo).

To further characterize TEAEs considered by the reporting investigator to be IARs, a summary table of TEAEs reported as IARs will be provided. The number and percentage of subjects who experienced IARs will be presented by SOC and by PT within SOC for each treatment group. A subject will be counted only once within the same SOC and within the same PT.

Summary of IARs will also be presented by severity, and for relationship to each treatment component (ATB200, AT2221, alglucosidase alfa, and placebo) as well as for the co-administration. Additional summary tables/plots will be provided to describe the clinical characteristics of the IARs by treatment group, including the event rates, changes in severity over time, and time to first IAR (see Section 9.4.1). The IAR summary will also be presented by prior history of IARs (yes/no), and by ERT status (experienced/naïve).

A listing of treatment-emergent IARs, serious IARs, IAR-related deaths, and IARs leading to study drug discontinuation will be provided. A listing displaying the summary of number of infusions and infusions associated with IARs by each individual subject who had an IAR will also be provided. For each subject, this listing provides subject ID, number of infusions received, number of infusions associated with IARs, percentage of infusions associated with IARs, the TEAEs that are IARs (IAR-TEAEs) occurring in each of the time intervals (see Section 9.1.4.2 and Section 9.1.4.3), and the event severity of the IARs corresponding to (or associated with) each infusion.

A summary of IAR-TEAEs by subjects with IARs, and the number of subjects with 1, 2, 3, 4 to 6, 7 to 10, 11 to 19, and ≥ 20 IARs will be summarized for each treatment group. A summary of the number of infusions and IARs associated with the infusions will be provided for all subjects as well as only for subjects who had IARs.

